9.2.5 Clinical Risks and Mitigation Strategy

A number of safety aspects have been built into the design of this study in light of the preclinical and clinical safety data with elenbecestat, and to mitigate clinical risk in the progression from 14 days of dosing in the MAD study to 18 months of Core Study treatment and 48 months of Extension Phase treatment in this Phase 2 study. (revised per Amendments 07 and 08) These safety aspects include the following:

- Immunology-related and infection-related exclusion criteria for both the Core Study and the Extension Phase (revised per Amendment 07)
- Review of unblinded safety data by an independent DSMB at regular intervals
- Safety criteria for study drug discontinuation based on CD4 (T helper cells), CD8 (cytotoxic T cells), CD19 (B cell) during the Core Study and absolute lymphocytes during the Extension Phase (revised per Amendment 07)
- Safety criteria for study drug discontinuation during the Core Study and Extension Phase based on skin rash, reoccurrence of herpes virus infections including any oral herpes, genital herpes or shingles, other infections, MRI changes, ECGs, and pregnancy. (revised per Amendment 07)

In addition to the features above, other safety aspects of this study designed to mitigate clinical risk include the following:

- Blinded safety data will be monitored by Eisai at regular intervals during the course of the Core Study
- Routine safety assessments will include the monitoring and recording of all AEs and SAEs, monitoring of hematology, blood chemistry, and urinalysis, measurement of vital signs, regular ECGs, physical and neurological examinations, and dermatological assessments at regular intervals. (revised per Amendment 07) AEs that might indicate signals of possible drug abuse potential will require a detailed follow-up. Subjects reporting AEs relating to abnormal dreams, nightmares, or sleep terror will be questioned on the frequency and impact of these events. To assess potential immunomodulatory effects, peripheral blood mononuclear cells (PBMCs) will be collected at baseline, during treatment, and posttreatment of the Core Study and at Extension Phase Baseline (Visit 21), 6 months (Visit 26), 12 months (Visit 28), and 24 months (Visit 32). (revised per Amendment 08)

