9.3.3 Removal of Subjects from Therapy or Assessment

The investigator may discontinue study drug or withdraw the subject from the study at any time for safety or administrative reasons. The subject may decide to stop study drug or withdraw from the study at any time for any reason.

Subjects who discontinue taking study drug prematurely for any reason will undergo an ED Visit within 7 days of their last dose of study drug (see [Section 9.1.2.2](#)). Follow-up Visits will also be scheduled 2, 4, 8, and 12 weeks after the last dose of study drug in the Core Study (see [Section 9.1.2.3](#)), and 4 and 12 weeks after the last dose of study drug in the Extension Phase (see [Appendix 6](#)). (revised per Amendments 04, 05, and 07)

The primary reason for discontinuation and all other reason(s) contributing to the subject's discontinuation from study drug(s) should be collected on the Subject Disposition eCRF page. In addition, the date of last dose of study drug(s) will be recorded on the Study Drug Dosing eCRF page. If a subject discontinues study drug and withdraws from the study at the same time, the ED Visit will be followed (see [Section 9.5.5](#)).

Safety-related criteria for discontinuation of study drug during the Core Study include the following: (revised per Amendments 07)

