- c. Subjects with clinical evidence of infection will have their CD4 (T helper cells), CD8 (cytotoxic T cells), and CD19 (B cells) absolute counts measured. Blood and other biological samples will also be collected for investigations of infective pathogens (eg, serological tests, quantitative polymerase chain reaction, microscopy, and culture) where appropriate. In subjects with infection, if any of their absolute cell counts meets the discontinuation thresholds, study drug will be discontinued. All subjects with severe

infections will be discontinued from study drug. All subjects with herpes zoster (shingles) or ocular herpes infections will be discontinued from study drug, regardless of severity of presentation. Subjects with mild or moderate infection may continue treatment with study drug unless otherwise clinically indicated or otherwise specified below. Specifically, when any of the CD4 (T helper cells), CD8 (cytotoxic T cells), and CD19 (B cells) absolute counts are between the population-adjusted LLN and the discontinuation thresholds, subjects with infections of moderate intensity will be discontinued from study drug (eg, subjects whose infections are not localized, or subjects who are systemically unwell, or who require systemic anti-infective drug treatment). All subjects with infection who are discontinued from study drug will be followed for a period of 12 weeks or until the infection resolves/stabilizes or until the CD4 (T helper cells), CD8 (cytotoxic T cells), and CD19 (B cells) absolute counts have returned to greater than population-adjusted LLN (whichever comes latest). (revised per Amendments 02 and 04)

Table 2 Study Drug Actions for Lymphocyte Subset Absolute Counts and Infection

| Criterion | Severity of Infection | | | |
|--|--|---|---|------------------------|
| | None | Mild | Moderate | Severe |
| CD4 (T helper cells), CD8 (cytotoxic T cells), or CD19 (B cells) absolute counts below discontinuation threshold | If confirmed with repeat testing within 1 week, then temporarily suspend study drug as per instructions above. | Discontinue study drug | Discontinue study drug | Discontinue study drug |

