| CD4 (T helper cells), CD8 (cytotoxic T cells), or CD19 (B cells) absolute counts between population-adjusted LLN and discontinuation threshold | May continue treatment with study drug unless discontinuation is clinically indicated | May continue treatment with study drug unless discontinuation is clinically indicated | Discontinue study drug | Discontinue study drug |
| CD4 (T helper cells), CD8 (cytotoxic T cells), or CD19 (B cells) absolute counts always > population-adjusted LLN | May continue treatment with study drug unless discontinuation is clinically indicated | May continue treatment with study drug unless discontinuation is clinically indicated | May continue treatment with study drug unless discontinuation is clinically indicated (See (e) for exception) | Discontinue study drug |

LLN = lower limit of normal.

(Table revised per Amendments 02 and 04)

- d. A subject with any skin rash of moderate to severe intensity, or any rash lasting more than 72 hours regardless of severity (see (e) for exception), will be discontinued from study drug and a dermatological consult will be requested regardless of whether the rash is considered drug-related or due to other causes. For cases where the investigator

suspects a drug rash, regardless of severity, the subject will be discontinued from study drug, a dermatological consult will be requested, and a skin biopsy will be performed to confirm the diagnosis. The skin rash will be treated as per standard care and will be followed up until resolution regardless of etiology or severity.

- e. Subjects who develop moderate to severe oral or genital herpes should be discontinued from study drug. Subjects who develop a mild case of oral or genital herpes may remain on study drug even if the event lasts more than 72 hours.

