- f. Development of any of the following features on MRI: vasogenic edema, macrohemorrhage, an area of superficial siderosis, or a symptomatic microhemorrhage. If discontinued from study drug, subjects will undergo an ED Visit within 7 days after discontinuation and will attend the Follow-up Visits 2, 4, 8, and 12 weeks after the last dose of study drug. They will also undertake an UNS Visit (with MRI) at approximately 4 weeks after the visit at which such MRI features were first identified. An MRI will also be performed at approximately the time of the final Follow-up Visit (Visit 20). Additional visits for safety may be arranged if clinically indicated in the opinion of the investigator, including after 12 weeks after the last dose of study drug. At any time during the Treatment Period, subjects who have asymptomatic, treatment-emergent microhemorrhages as detected by MRI, but none of the features which merit discontinuation of treatment (ie, vasogenic edema, macrohemorrhage, an area of superficial siderosis, or a symptomatic treatment-emergent microhemorrhage) may continue with treatment. These subjects will have safety assessments (including MRI) at approximately 4 weeks after the visit at which such MRI features were found. They will also continue with the scheduled MRI scans. Additional unscheduled MRI scans may be arranged on an individual subject basis in discussion with the study medical monitor. (revised per Amendment 04)
- g. A postdose ECG with an average QTcF interval >500 msec from triplicate ECGs
- h. A postdose ECG with a QTcF interval increase from baseline >60 msec and a QTcF interval >450 msec as demonstrated from triplicate ECGs
- i. Any seizure (motor or non-motor)
- j. Pregnancy

Safety-related criteria for discontinuation of study drug during the Extension Phase are provided in [Appendix 6](#). (revised per Amendment 07)

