The primary reason for discontinuation and all other reason(s) contributing to the subject's discontinuation from study drug should be collected on the ED from study drug electronic case report form (eCRF) page (see Protocol [Section 9.5.5](#)). In addition, the date of last dose of study drug will be recorded on the Study Drug Dosing eCRF page.

Safety-related criteria for discontinuation of study drug include the following:

1. Absolute lymphocyte count will be monitored during the study. Should a subject develop lymphocytopenia (less than $800/\text{mm}^3$ or LLN, whichever is higher), a confirmation test should occur as soon as possible but no later than within 5 days with a repeat test of absolute lymphocytes. If confirmed, study drug administration should be interrupted for a minimum period of 2 weeks. Restart of study drug may take place only when absolute lymphocyte count returns to greater than LLN. Absolute lymphocyte count will be measured 4 weeks after restart of study drug. Subsequent measurements of absolute lymphocyte counts will follow the schedule of assessments and any results showing a Grade 2 or greater lymphocytopenia (less than $800/\text{mm}^3$) should be handled as above. If a 2nd occurrence of Grade 2 or greater lymphocytopenia (less than $800/\text{mm}^3$), that is confirmed on repeat testing, occurs within 6 months, then the subject should be discontinued permanently from the study drug.
2. A subject with any skin rash of moderate to severe intensity, or any rash lasting more than 72 hours regardless of severity (with the exception of oral or genital herpes as described in the next paragraph), will be discontinued from study drug and a dermatologic consult will be requested regardless of whether the rash is considered drug-related or due to other causes. For cases where the investigator suspects a drug rash, regardless of severity, the subject will be discontinued from study drug, a dermatologic consult will be requested, and a skin biopsy will be performed to confirm the diagnosis. The skin rash will be treated as per standard care and will be followed up until resolution regardless of etiology or severity.
3. Subjects who develop moderate to severe oral or genital herpes should be discontinued from study drug. Subjects who develop a mild case of oral or genital herpes may remain on study drug even if the event lasts more than 72 hours.
4. Pregnancy

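### Section 9.2.5 promises Extension Phase stop criteria for shingles and other infections, but the Appendix 6 list has none for severe infection or ocular herpes and reaches shingles only through its rash rule

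*Protocol*

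**What the plan says.** Section 9.2.5 lists the safety features meant to reduce clinical risk. One bullet says that there are discontinuation criteria for the "Core Study and Extension Phase based on skin rash, reoccurrence of herpes virus infections including any oral herpes, genital herpes or shingles, other infections", and goes on to MRI changes, ECGs and pregnancy.

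The criteria themselves are in two separate lists. Section 9.3.3 opens its list with "Safety-related criteria for discontinuation of study drug during the Core Study include the following" and closes with "Safety-related criteria for discontinuation of study drug during the Extension Phase are provided in" Appendix 6. Sites therefore take Core Study stops from Section 9.3.3 and Extension Phase stops from Appendix 6.

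On infection, Section 9.3.3(c) is explicit: "All subjects with severe infections will be discontinued from study drug", and "All subjects with herpes zoster (shingles) or ocular herpes infections will be discontinued from study drug, regardless of severity of presentation". It adds stops that depend on CD4, CD8 and CD19 counts in subjects with infection.

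Appendix 6 has seven items. Item 2 covers moderate to severe rash and "any rash lasting more than 72 hours regardless of severity (with the exception of oral or genital herpes as described in the next paragraph"). Item 3 reads "Subjects who develop moderate to severe oral or genital herpes should be discontinued from study drug". The others are lymphocytopenia, pregnancy, a QTcF increase, MRI features, and QTcF above 500 msec.

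**The concern.** The bullet in Section 9.2.5 says that an infection-based stop exists in both phases, and the Extension list does not contain one. The bullet before it separates the two phases carefully (lymphocyte subsets in the Core Study, absolute lymphocytes in the Extension Phase), so joining the phases here does not look like leftover Core Study wording.

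Infection is the main immunological risk that this section addresses. Section 7.2 links reductions in CD4 and CD8 counts at 200 and 400 mg to possible relapse of orolabial herpes or other infections. A site following Appendix 6 to the letter could keep a subject on 50 mg through a severe infection, or through ocular herpes without a qualifying rash, while the protocol tells ethics committees and investigators that a stop criterion is in place.

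**Working it through.** No arithmetic underlies the main point. The check sets the triggers named in Section 9.2.5 against the two operative lists.

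| Trigger named in 9.2.5 for both phases | Core Study, Section 9.3.3 | Extension Phase, Appendix 6 |
|---|---|---|
| Skin rash | (d) | item 2 |
| Oral or genital herpes | (e), moderate to severe | item 3, moderate to severe |
| Shingles | (c), any severity | no item of its own; item 2 only |
| Other infections | (c): all severe infections, ocular herpes at any severity, and count-dependent stops | none |
| MRI changes | (f) | item 6 |
| ECG | (g), (h) | items 5 and 7 |
| Pregnancy | (j) | item 4 |

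The three Core Study infection stops that do not depend on cell counts then fare as follows in the Extension Phase.

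1. **Severe infection.** No Appendix 6 item mentions it. Item 1 is a laboratory rule on absolute lymphocytes with no infection element.
2. **Ocular herpes.** Item 3 is limited to oral and genital herpes. Item 2 applies only if there is also a qualifying skin rash.
3. **Shingles.** Item 2 exempts only oral and genital herpes, so a shingles rash counts. The cases that escape are mild eruptions lasting 72 hours or less.

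Appendix 6 therefore names 0 of 3; 2 of 3 have no criterion and 1 of 3 is mostly covered.

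The count-dependent Core Study rules cannot fill the gap. In the Extension Phase, lymphocyte subsets are measured only in the first 12 months, and under Appendix 6 (Table 13, note b) the reports do not go to sites.

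Entry rules show the inconsistency from another side. Ophthalmic shingles or ocular herpes simplex arising after Core Study screening bars a subject from the Extension Phase, as does active infection within 4 weeks of Visit 21. The same ocular herpes appearing just after Visit 21 meets no stop criterion.

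The maximum exposure is 208 weeks of Extension treatment, against 78 weeks in the Core Study (208/78 = 2.7). This is a ratio of treatment durations, not of risk.

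The same bullet contains a smaller mismatch. It refers to any oral or genital herpes, while Section 9.3.3(e) says "Subjects who develop a mild case of oral or genital herpes may remain on study drug", and Appendix 6 item 3 also stops only moderate to severe cases.

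**The case against.** Section 9.2.5 is a design discussion, not an instruction to sites, and both operative lists are introduced in a way that does not claim to be exhaustive. Appendix 6 is also clearly not a truncated copy of Section 9.3.3. It swaps subset thresholds for absolute lymphocytes, omits the seizure stop, and turns the MRI and QTcF above 500 msec stops into discussions with the medical monitor. A deliberately lighter Extension list is therefore possible.

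Other safeguards apply. The investigator may stop drug at any time for safety. Section 9.4.1 asks for discussion with the medical monitor about suspending drug during a concurrent illness. Severe infection and herpes zoster require detailed information to the medical monitor (Section 9.5.1.5.1), and ocular herpes is always reported as serious (Section 9.5.1.5.2). Section 9.4.4 adds that no subject in Study 002 had an infection while receiving 100 mg or less.

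Much of this stands as a limit on the likely harm: most investigators would stop drug for a severe infection anyway. It does not remove the contradiction. Discretion, temporary suspension and reporting are not discontinuation criteria, and a non-exhaustive list cannot tell a site which infections require stopping.

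On intent, the revision history for Amendment 08 records the MRI and QTcF changes and gives a reason, but records no removal of infection stops. The entry for Amendment 07 says that the safety features were extended to the open-label phase. Omission is the more natural reading. If it was intended, Section 9.2.5 is wrong instead.

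**Conclusion.** The concern holds and should be corrected. The current text states that the Extension Phase has stop criteria for shingles and other infections. The only Extension list has no criterion for severe or other infection or for ocular herpes, and only an indirect, nearly complete one for shingles. The firm gap is severe infection and ocular herpes; the shingles gap is narrow. The oral and genital herpes wording is minor, and the conclusion does not depend on it or on the duration ratio.

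The conclusion rests on reading Appendix 6 as the sole Extension list, as Section 9.3.3 directs. No mandatory infection stop for the Extension Phase was found elsewhere in the protocol. How many subjects would be affected cannot be derived from the document.

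**What to change.** Add one item to the Appendix 6 discontinuation list: study drug is discontinued for any severe infection, for herpes zoster of any severity, and for ocular herpes of any severity. This carries over the existing Section 9.3.3(c) stops that need no subset counts, so sites can apply it.

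If the sponsor dropped these stops on purpose, limit the Extension part of the Section 9.2.5 bullet to what Appendix 6 contains: skin rash, moderate to severe oral or genital herpes, pregnancy, and MRI and ECG findings as items 5 to 7 word them. Shingles and other infections would then be stated for the Core Study only.

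In either case, change the oral and genital herpes wording in Section 9.2.5 to moderate to severe cases.

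The cost is one item and one bullet within an amendment. Each additional subject stopped would have the Early Discontinuation Visit (with MRI if none was done in the preceding 90 days) and the Week 4 and Week 12 Follow-up Visits that the protocol already requires after any discontinuation. No new procedure or analysis is needed.

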9.3 Selection of Study Population

Approximately 60 ($\pm 20\%$) eligible MCI/Prodromal or mild to moderate AD subjects will be randomized at approximately 35 sites in the United States (revised per Amendments 02 and 04). There will be no restriction to the number of subjects from either population.

Subjects who do not meet all of the inclusion criteria in [Section 9.3.1](#) or who meet any of the exclusion criteria in [Section 9.3.2](#) will not be eligible to receive study drug during the Core Study. Subjects who do not meet all of the inclusion criteria or who meet any of the exclusion criteria provided in [Appendix 6](#) will not be eligible to enter the Extension Phase. (revised per Amendment 07)

9.3.1 Inclusion Criteria

Subjects must meet all of the following criteria to be included in this study:

1. Meets the core clinical research criteria of the NIA-AA for MCI due to AD ([Albert, et al., 2011](#)) or AD dementia ([McKhann, et al., 2011](#)) and is "staged" or classified as either MCI or mild to moderate dementia and also complies with the following: (revised per Amendment 01)

Required at Screening Visit 1:

(revised per Amendment 02)

- a. Subjective Memory Complaint with evidence of concern about a decline in cognition from the subject, informant, or clinician's observation
 - b. Cognitive impairment of at least 1 SD from age adjusted norms in delayed recall on the ISLT. Alternatively, cognitive impairment of at least 0.5 SD from age-adjusted norms in delayed recall on the ISLT plus impairment of at least 1 SD from age-adjusted norms in at least 1 other computerized learning and memory test (ISLT immediate recall, or 1 of the learning and memory components of the CBB). (revised per Amendment 02)
 - c. FAQ ≤ 24 (revised per Amendment 01)
 - d. MMSE ≥ 16 (revised per Amendment 01)
2. Amyloid positive PET image based on centralized PET scan reading; an historical amyloid positive PET scan may be used if conducted within the previous 12 months and provided that the scan and result are considered acceptable by the central PET reading group (revised per Amendment 02)
 3. Male or female, age 50 to 85 years, inclusive at time of consent
 4. Must have an identified caregiver or informant who is willing and able to provide follow-up information on the subject throughout the course of the study. This person must, in the opinion of the investigator, spend sufficient time with the subject on a regular basis such that the caregiver or informant can reliably fulfill the study requirements and must provide separate written consent. The caregiver or informant need not be living in the same residence as the subject. If the caregiver or informant is not residing with the subject, the investigator has to be satisfied that the subject can contact the caregiver or informant readily during the times when the caregiver or informant is not with the subject. If in doubt about whether a subject's care arrangements are suitable for inclusion, the investigator should discuss this with the medical monitor. At visits where the CDR or FAQ are conducted, caregivers or informants need to either attend the visit in person along with the subject or be able to be contacted by telephone at the time of the visit. The investigator will determine whether attendance in person is required or whether telephone contact will be suitable and will base this determination upon the functional ability of the subject among other factors.
 5. If receiving acetylcholinesterase inhibitors (AChEIs) or memantine, must have been on a stable dose for at least 12 weeks before the Baseline cognitive assessments at Visit 2, with no plans for dose adjustment in the foreseeable future. Treatment-naïve subjects can be entered into the study but there should be no plans to initiate treatment with AChEIs or memantine at the time of entry into the study.

6. Must have been on stable doses of all other permitted chronically used concomitant medications (ie, not related to their cognitive decline) for at least 4 weeks before randomization

